15.5.5. Safety Analysis

The safety analyses will be performed using the mITT Population.

An overall summary of AEs will be provided including the number of events and percent of subjects with any AEs, SAEs, and UADEs. For each type of event, the number of events and number and percent of subjects with the event will be provided in a table. Separate summaries of all adverse events will be summarized by relationship to device and procedure. Adverse events will be coded using MedDRA medical dictionary.

15.5.6. [REDACTED]

[REDACTED]

[REDACTED]

[REDACTED]

[REDACTED]

[REDACTED]

[REDACTED]

[Redacted]

15.5.7. [Redacted]

[Redacted]

[Redacted]

[Redacted]

[Redacted]

[Redacted]

[Redacted]

[Redacted]

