5. STUDY DESIGN

5.1. Study Design

This is a multicenter, prospective, randomized, parallel design, double-blinded, sham-controlled study. A total of 270 subjects are planned for the pivotal study cohort. Subjects meeting the general inclusion/exclusion criteria will undergo baseline endoscopic assessment. Those who meet endoscopic eligibility will be randomized in a 2:1 allocation to the Treatment or Control group stratified according to center. The Treatment group will receive the TPS placement and the Control group will receive a sham endoscopic procedure that does not include TPS placement.

Subjects will be followed up for 12 months after the index procedure or until the device is removed.

[figure not shown]
At 12 months, subjects in the Treatment group will undergo an endoscopic assessment followed by the TPS removal. Subjects in the Control group will complete all the same assessments as the Treatment group except the endoscopy.

Subjects who achieve a BMI of ≤ 22 kg/m² for two consecutive visits before the 12-months follow up will be considered a treatment success, have the device removed if in the Treatment group, and exit the study. A BMI of 22 kg/m² is selected as a reference value since it is a midpoint value of the normal BMI range, and a BMI ≥ 23 kg/m² has been shown to be associated with an increased risk of developing diabetes in the Nurses' Health Study that followed 43,581 women over 8 years.²⁸ The handling of these subjects in the analysis is described in Section 15.5.

Subjects in both groups will receive the same lifestyle modification education and counseling during the 12-month follow up duration. In brief, subjects will receive written instruction in lifestyle modification strategies for weight loss (e.g., caloric restriction, increasing physical activity, behavioral modification, etc.) at the beginning of the study. At each follow up visit, subjects will receive a brief (15 minute) lifestyle modification counseling performed by a medical provider (i.e., registered dietitian, nurse, behavioral health specialist)

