7.5. Patient Discontinuation

Once enrolled, each subject will remain in the study until the required follow-up period is complete. However, the subject has the right to withdraw from the study at any time without penalty or loss of benefit. The following events will result in terminating the subject's follow-up:

- Subject voluntary withdrawal
- Subject withdrawn by the Investigator as clinically indicated
- Subject becomes pregnant
- Subject lost to follow-up
- Subject death
- Study is terminated according to Section 5.6 (Early Study Termination)

In the case of subject withdrawal from the study, the TPS must be removed before the subject exits the study.

In case the TPS is removed early as described in Section 10.5, the subject's participation in the study is considered terminated. Any Adverse Events will be followed until resolution or stabilization according to Section 12.1.

In case a subject achieves normal BMI (≤ 22 kg/m²) for two consecutive visits before the 12-month follow up, the subject is considered to have completed the study. Subject will exit the study and the device should be removed in the treatment subjects.

A final endoscopy should be performed whenever possible before the Treatment subject exits the study.

The Sponsor must be notified of the reason for subject discontinuation. The site will document this information on the electronic case report form (eCRF) and make every effort to give a full description of the reason for withdrawal. Investigators must also report this information to the local IRB as defined by their institution's procedure.

Subjects who are terminated early will not be replaced by enrolling additional subjects.

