10.2. Managing Endoscopic Observations

Tissue effects such as erythema, erosions, or ulcers may be observed during endoscopic surveillance. Limited clinical experience to date suggests that some patients may be asymptomatic while others may develop symptoms.

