Before the subject is discharged, s/he is to be provided with a subject information card. This card provides the phone number and name of the person to contact in case s/he needs medical attention related to the therapy. Additionally, the subject can provide this card to an emergency room doctor, allowing them to contact the Primary Investigator and obtain information about the study. A sample of the card is provided in Appendix G.

The subject should be placed on a liquid diet for 3 days, followed by soft food for a week, slowly returning to normal food in 10 days.

The following procedures/assessments will be performed during this visit:

- Abbreviated physical examination including vital signs (temperature, systolic/diastolic blood pressure, respiration rate, heart rate)
- Body mass assessment (body weight, calculation of BMI, and measurement of circumferences)
- Assessment of medications
- Endoscopic assessment
- Confirmation of eligibility
- TPS placement procedure

- Assessment of AEs that occurred during the procedure

Post-Procedure Follow-Up Visits

Post-procedure follow-up visits are summarized in Appendix B. They include:

- Office visits at 1 week, and 1, 2, 4, 6, 9, 12 months
- Endoscopic assessments at 2, 6, and 12 months
- Visual Analog Scale assessment at 1 week and 1, 6, and 12 month(s)
- Eating Inventory assessment at 1 week and 1, 6 and 12 month(s)
- Blood tests at 6 and 12 months
- IWQOL-Lite at 6 and 12 months
- Device removal at 12 months
- AE assessments at each follow-up visit
- Brief lifestyle counseling at each follow-up visit and brief telephone calls at 7, 8, 10, and 11 months.

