11.9.10. Twelve-Month Post-Index Procedure (365 ± 30 Days)

The following data are to be collected:

- Physical examination

- Body mass assessment (body weight, calculation of BMI, and measurement of circumferences)
- Concomitant medications
- IWQOL-Lite
- Visual Analog Scale assessment
- Eating Inventory assessment
- Blood tests (lipid levels and lipoproteins, glucose, insulin, HbA1c, high sensitivity C-reactive protein)
- Endoscopic assessment
- Assessment of AEs that occurred since the last visit
- Assessment of blinding
- Brief lifestyle counseling
- Unblinding and Pivotal study exit

The above data are to be collected prior to unblinding with the exception of the endoscopic assessment, which is to be collected at the time of removal.

Subjects who were assigned to the Control group will not require an endoscopy at this visit since device removal is unnecessary but they should remain blinded until the all other data are collected.

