11.9.10.1. TPS Device Removal

The TPS is to be removed 365 ± 30 days after the index procedure under general or MAC anesthesia. An endoscopic assessment will be performed in all subjects followed by TPS removal in the Treatment group. The device removal procedure is described in detail in the IFU 

Subjects will be discharged according to the hospital and physician's discharge criteria.

All procedure- and device-related AEs must be followed until resolution or stabilization (the Investigator does not expect any further improvement or worsening of the event). Following study exit, follow-up will be according to clinical practice.

Subjects will be informed that his/her participation in this study is complete. The subject's study exit will be documented.

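### Sections conflict on whether Controls have a 12-month endoscopy; if they do not, section 15.5.5 has no means of keeping silent lesions seen only in the Treatment arm apart from other adverse events

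*Combined protocol and SAP*

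**What the plan says.** **Who is examined at 12 months.** Section 5.1 (Study Design) says: "Subjects in the Control group will complete all the same assessments as the Treatment group except the endoscopy". Section 11.9.10 agrees and gives a reason: "Subjects who were assigned to the Control group will not require an endoscopy at this visit since device removal is unnecessary". Section 11.9.10.1 (TPS Device Removal), covering the same 365 ± 30 day window, says the opposite: "An endoscopic assessment will be performed in all subjects followed by TPS removal in the Treatment group".

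**Who is examined at early exit.** Section 7.5 (Patient Discontinuation) says: "A final endoscopy should be performed whenever possible before the Treatment subject exits the study". It has no counterpart for Controls.

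**Earlier endoscopies.** The list of follow-up visits in section 11.9.3 gives "Endoscopic assessments at 2, 6, and 12 months" and names no arm.

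**Silent lesions.** On erythema, erosions and ulcers, section 10.2 says: "Limited clinical experience to date suggests that some patients may be asymptomatic while others may develop symptoms".

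**The tables.** Section 15.5.5 uses the mITT population and says: "For each type of event, the number of events and number and percent of subjects with the event will be provided in a table". It adds summaries by relationship to device and to procedure. Its visible text sets no time window, does not separate events by how they were found, and does not itself mention the arms. The arm split comes from section 15.1, which calls for summaries by treatment group, and by visit where appropriate.

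**The concern.** A lesion without symptoms is recorded only if someone looks. If one arm is examined at 12 months and at exit and the other is not, the arms differ in their chance of having a lesion counted, whatever the device does. The sham arm is the trial's only background reference for such lesions. A reader who sets the two percentages side by side would read a difference in examination as a difference in harm.

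Section 12 bases the risk-benefit assessment on the adverse event profile, so a distortion in a purely descriptive table still matters. It would make the device look worse on these rows.

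**Working it through.** **1. The plan's own safety figures.** The documents give no figure for this asymmetry. The safety precision figures in section 15.4 reproduce:

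- Chance of at least one event at a 0.9% rate in 180 subjects: 1 − (1 − 0.009)^180 = 80.4% (stated: 80%).
- Upper limit of the two-sided exact 95% interval for 0 of 180: 1 − 0.025^(1/180) = 2.03% (stated: 2.0%).

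Both describe precision within the Treatment arm. Neither concerns comparability between arms.

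**2. The sections side by side.**

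| Occasion | Treatment | Control |
|---|---|---|
| 2 and 6 months (11.9.3) | Listed | Listed without naming arms |
| 12 months (5.1, 11.9.10) | Yes | No |
| 12 months (11.9.10.1) | Yes | Yes |
| Early exit (7.5) | Where possible | Not mentioned |

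If 11.9.10.1 describes the intended conduct, the 12-month gap closes, but the early-exit gap in 7.5 remains. If 5.1 and 11.9.10 do, both gaps stand.

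**3. Would these lesions enter the table?** Section 12.1 says that scheduled endoscopies are not themselves adverse events. It does not exclude what they reveal. Section 12.1.1 says only that findings managed by medication and surveillance are not serious. I therefore take such lesions to be non-serious adverse events. The documents do not state this outright.

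**4. Illustration with no device effect.** Assumptions, none of them from the documents:

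- r is the proportion with a lesion already detected, the same in both arms.
- q is the chance, among the rest, of a lesion visible only at the 12-month endoscopy, also the same in both arms.
- Every Treatment subject is examined at 12 months and no Control is.

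Expected percentage in Treatment = r + (1 − r)q. Expected percentage in Control = r.

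| r | q | Treatment | Control | Ratio |
|---|---|---|---|---|
| 5% | 2% | 0.05 + 0.95 × 0.02 = 6.9% | 5% | 1.38 |
| 5% | 5% | 0.05 + 0.95 × 0.05 = 9.75% | 5% | 1.95 |
| 5% | 10% | 0.05 + 0.95 × 0.10 = 14.5% | 5% | 2.90 |
| 10% | 2% | 0.10 + 0.90 × 0.02 = 11.8% | 10% | 1.18 |
| 10% | 5% | 0.10 + 0.90 × 0.05 = 14.5% | 10% | 1.45 |
| 10% | 10% | 0.10 + 0.90 × 0.10 = 19.0% | 10% | 1.90 |

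With the planned 180 and 90 subjects and r = 5%, the expected number of subjects with a lesion is 180 × 0.069 = 12.4 to 180 × 0.145 = 26.1 in Treatment, against 90 × 0.05 = 4.5 in Control. At equal rates Treatment would have 180 × 0.05 = 9.

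**5. After the fix.** If the comparison is limited to endoscopies performed in both arms, both expected percentages are r and the spurious difference is 0.

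**The case against.** The strongest case on the other side has five parts.

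- **Section 11.9.10.1 may govern.** If so, the 12-month asymmetry disappears. This stands, and it is why reconciling the sections comes first.
- **Attribution does not rest on subtracting arms.** Causality is graded event by event (12.2), the CEC judges device relationship as if every subject had the device (13), and 15.5.5 tabulates by that relationship. This protects the judgement of lesions that are found. It cannot recover Control lesions that nobody looked for.
- **The data can already be split.** Section 10.2.1 classifies ulcers as symptomatic or asymptomatic, section 12.1 collects onset dates, and section 15.1 allows tables by visit. This lowers the cost of the fix. But the ulcer classification does not cover erosions or erythema and commits to no table, and 15.1 permits a by-visit table without requiring one.
- **The impact is limited.** Section 6.3 plans no formal safety test, the affected rows are mainly non-serious, and the bias cannot hide harm from the device. All of this stands.
- **The assumed rates may be high.** Subjects take a PPI, must be negative for *H. pylori*, stay off NSAIDs (low-dose aspirin aside) and have no peptic ulceration at entry. This is fair: at q = 1% and r = 5% the table would show 0.05 + 0.95 × 0.01 = 5.95% against 5%.

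A reader might go further than the documents allow in two ways. One is to say that 15.5.5 prescribes a single whole-study percentage by arm. It does not: the arm split comes from 15.1, and pooling over time is inferred from the lack of a stated window. The other is to infer that Controls have no follow-up endoscopy at all, so that coverage is three against none. The 11.9.3 list names no arm, and the endoscopic schedule in the protocol summary is redacted. In Appendix B, the footnote for the Treatment group only has no visible anchor. That inference would rest on text nobody outside can read.

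**Conclusion.** The point holds conditionally. The sections on the 12-month endoscopy contradict each other and must be reconciled. If Controls are not examined then, silent lesions seen only at the 12-month or exit endoscopy can be found in Treatment alone, and the visible text of 15.5.5 does not keep them apart from other adverse events.

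The result is an inflated Treatment excess in mainly non-serious lesion rows. The size is illustrative only: 6.9% to 14.5% against 5% with no device effect, for r = 5% and q from 2% to 10%. It shrinks to nothing as q approaches zero. The conclusion also assumes that silent lesions are recorded as adverse events and that nothing in the redacted sections (5.4, 5.5, 15.5.6, 15.5.7) already separates them. It affects the descriptive reading by arm and the section 12 risk-benefit assessment, not any planned test. It does not mean that device attribution is impossible, since causality is still assessed for each event.

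**What to change.** First, reconcile sections 5.1, 7.5, 11.9.10 and 11.9.10.1 on who is examined at 12 months and at early exit.

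Then add to section 15.5.5:

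- Tabulate lesions found only at a scheduled or exit endoscopy separately from symptomatic or otherwise clinically detected events.
- Present them by endoscopy visit, with the number of subjects examined as denominator.
- Compare arms only for endoscopies performed in both arms.
- If Controls are not examined at 12 months or at exit, label those findings as single-arm.

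The cost is SAP wording and one extra table, with no added procedure. The sponsor should confirm that the means of detection can be derived for erosions and erythema. For ulcers, the symptom classification in section 10.2.1 and the onset date in section 12.1 are already planned.

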15.5.8. Assessment of Poolability

The poolability of the study results across study sites will be assessed. A regression model with covariates for study site, treatment group, and site*treatment interaction will be fit. Study sites with fewer than 10 subjects will be combined into a single pseudo-site for this analysis. If the p-value for the site*treatment interaction term is < 0.10 , this will be considered statistical evidence of a potential differential treatment effect by site.

16. QUALITY CONTROL AND QUALITY ASSURANCE

16.1. Selection of Study Sites and Investigators

The Sponsor will select Investigators who are qualified by training and experience to perform clinical research in this field and to participate in the clinical investigation. Sites will be selected based upon an assessment of the qualifications of the Primary Investigator and the facilities at each site. All Investigators will be trained on the device, the protocol and all study procedures prior to enrolling subjects.

A pre-investigation visit will be conducted at each study site to assure that the Investigator and the study staff understand the obligations for using and managing the investigational device, following the study protocol, obtaining informed consent, adhering to FDA and IRB regulations, and conducting clinical research.

16.2. Training

16.2.1. Site Training

All Investigators/study personnel are required to attend Sponsor training sessions, which may be conducted at an Investigator's meeting, a site initiation visit or other appropriate training sessions. Remote over-the-phone or web-based training will take place as necessary. Training of Investigators/study personnel will include, but is not limited to, the investigational plan, participant recruitment, enrollment (including review of inclusion and exclusion criteria), subject retention, investigational device usage, protocol requirements, case report form completion, and study personnel responsibilities. At least one individual at each site also will be trained in the delivery of the lifestyle modification counseling and the behavioral/psychosocial assessment by a consultant with relevant expertise. All Investigators/study personnel that are trained must sign a training log (or an equivalent) upon completion of the training. Investigator/study personnel must not perform any study-related procedures prior to being trained.

Investigators who perform the device placement/removal procedures will be trained on device use. BAROnova personnel will provide in-person technical support for a minimum of the first five procedures at each site.

16.2.2. Monitor Training

The Sponsor or designee will engage monitors that are qualified by appropriate training and experience to review the conduct and quality of the study. Prior to working on the study, monitors will be trained to the investigational plan, case report forms, and the device/procedure knowledge. Such training will be documented.

16.3. Study Monitoring

BAROnova and/or a designee (e.g., a Contract Research Organization), will monitor the clinical study in a manner consistent with FDA regulations and the Good Clinical Practice (GCP) standards adopted by BAROnova.

The Investigator is required to ensure compliance with all procedures required by the Investigational plan and by study procedures provided by the Sponsor. The Investigator agrees to provide reliable data and all information requested by the Investigational Plan including eCRFs, Discrepancy Clarification Forms or other appropriate instrument according to the instructions provided, and to ensure direct access to source documents to Sponsor representatives.

Clinical Monitors will periodically monitor all eCRFs and corresponding source medical records for each subject. The monitoring visits provide the Sponsor with the opportunity to evaluate the progress of the study, to verify the accuracy and completeness of eCRFs, to resolve any inconsistencies in the study records, and to

ensure that all protocol requirements, applicable regulatory regulations, and Investigator's obligations are being fulfilled. Monitoring and data verification may be performed remotely or onsite.

The Investigator and his/her staff will be expected to cooperate with Sponsor's personnel or designee and to be available during the monitoring visits to answer questions sufficiently and to provide any missing information.

16.4. Source Data Verification

Source data verification ensures accuracy and credibility of the data obtained. During monitoring, reported data are reviewed with regard to being accurate, complete, and verifiable from source documents (e.g., subject files, physician notes, discharge summaries, operative records, study worksheets, etc.). All data reported on the eCRF should be supported by source documents, unless the eCRF also serves as a source document.

16.4.1. Definition of Source Data

Source data includes all information in source documents (original records, certified copies of original records, appointment books, original laboratory records, and original data recorded on customized worksheets) and includes all original recordings or copies of clinical findings, observations, or other activities in a clinical study necessary for the reconstruction and evaluation of the study. Certain data may be directly entered into eCRF. In this case, the eCRF serves as source document.

16.5. Direct Access to Source Data/Documents

The Investigator(s)/institution(s) will permit direct access to source data/documents for study-related monitoring, audits, IRB/IEC and regulatory inspection(s).

Consenting subjects are agreeing to allow the Sponsor or designee access and copying rights to pertinent information in their medical records relevant to study participation. As part of the informed consent, the Investigator or designee will obtain permission for regulatory authorities to review any records identifying subjects in this study. Sponsor will not otherwise release any personal information (refer to Section 18.3 Confidentiality).

16.6. Maintain Blinding during the Study

Only the data management organization and the unblinded statistician have access to the randomization code. The Sponsor's study management team, the Study Steering Committee, the CEC, and the statistician who is responsible for study design and data analysis will be blinded to subject's treatment during the study. The monitors from the monitoring organization will have access to subjects' treatment information in order to perform study monitoring and source data verification.

At each site, the Investigator who performs the index procedure and endoscopic follow up will not collect the outcome data. The Investigator or study coordinator who collects outcome data will be masked. Source documents containing subject treatment information will be either masked or access-controlled according to each site's practice. Each site's blinding procedure will be assessed by the study monitors at the monitoring visits.

In exceptional circumstances when knowledge of the Investigational Device is essential for patient safety in case of serious adverse event, the blinding for this subject may be broken.

The Investigator should promptly (within 24 hours) document and explain to the Sponsor any premature unblinding (e.g., accidental unblinding, unblinding due to a serious adverse event) of the study subject.

